Consistent with the disappointing findings for colorectal cancer, a number of large-scale clinical trials over the past half year reported no protective effects and, possibly even adverse effects in several cases, for supplementation with vitamins C, D, and E, selenium, calcium, and folate on not only colorectal cancer, but also prostate, breast or total cancer. The only beneficial effect was reported in a clinical trial conducted in China with supplementation in the Dietary Reference Intake (DRI) range. In a very recent commentary in *JNCI*, internationally renowned investigators in the field commented that growing evidence suggests that some nutrients or metals, including calcium, showed protective effects at normal range, but showed opposite effects at a high dose. Before the initiation of new large-scale intervention trials, it is essential to “rethink” the mechanisms, study design and dose-range of supplementation by conducting smaller-scale studies to understand nutrient-nutrient and gene-nutrient interactions, particularly in early tumorigenesis. Our proposed study is designed in such a manner to address many of the issues raised in the commentary, such as using biomarkers related to earlier tumorigenesis, supplementation of magnesium will not exceed the DRI for supplemental magnesium intake by more than 40 mg, supplementation dosage according to baseline dietary intake, nutrient-nutrient interaction (calcium/magnesium balance), and gene-nutrient interaction. Our findings may eventually lead to personalized strategies in the prevention of colorectal cancer and, perhaps, many other cancers or chronic diseases which are both linked to magnesium deficiency and common in Western societies.

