Dietary Intake Assessment Protocol

We have collected a FFQ in the TCPS (IRB # 090235). In this study, we will perform two baseline 24-hour dietary recall assessments for each participant to update intake information during the introductory phase of the study prior to the supplementation of magnesium. The assessments will take place by telephone and will include one weekday and one weekend day where possible. The Ca/Mg intake ratio will be calculated from the 24-hour recalls to confirm the current ratio, to determine eligibility, and to determine the appropriate dose of magnesium supplementation in the treatment arm to reduce the ratio to < 2.6 or the number of placebo capsules in the placebo arm. They will also be used to verify the dietary Ca/Mg intake ratio, excluding any treatment magnesium, remains stable throughout the intervention period. Thus participants will also complete 4 additional 24-hr dietary assessments during the intervention phase; 2 times of diet recalls at week 1 - 6, and 2 times at week 7-12 throughout the course of the magnesium treatment.

Dietary intake will be measured using the 24-hour recall (24HR) assessment approach. The 24HR is the least biased method of dietary assessment during an intervention. Compared to a food record or food diary, the 24HR is less time consuming for the participant, and does not rely on their concentration and recording skills. The 24HR approach is interviewer based, and the interviewer is able to probe as needed. Therefore, dietary monitoring is not as reliant on the personality attributes of the study participant. Nutrient scores from multiple 24HRs are highly correlated with nutrient scores from a food record, and the total variance of nutrient scores from multiple 24HRs is smaller than the variance derived from food records.

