The goal of this study is to evaluate the main effect on carcinogenesis related biomarkers, inflammatory biomarkers and magnesium status by reducing the dietary Ca/Mg intake ratio to under 2.6 by magnesium supplementation on carcinogenesis related biomarkers, inflammatory biomarkers and magnesium status and to estimate the potential interaction between magnesium treatment and the Thr1482Ile polymorphism (G→A) of the *TRPM7* gene. The study will enroll 288 participants with colorectal hyperplastic polyp or/and adenoma, polyps free but being at high risk of colorectal polyps or cancer, 152 of whom have the GG genotype and 136 of whom have GA/AA genotype. These participants will be randomized to either treatment or placebo using a double-blind two-factorial (Ca/Mg intake ratio and genotype) design so that each treatment/placebo arm will contain 60 participants with the GG genotype and 60 participants with at least one A allele. Based on the participant's Ca/Mg intake ratio (obtained from the two 24-hour recalls), he or she will be assigned to a dose that will reduce the Ca/Mg intake ratio to around 2.3 (less than 2.6 but no less than 2.0). The dose of magnesium supplementation is personalized based on the current intake ratio. The duration of the study from recruitment through the end of the intervention is approximately 14 weeks including a 12-week intervention. (See attached Figure E2)

The trial will be double-blind: neither participants nor research staff who interacts with the participants or their samples will be aware of the treatment assignments. The treatment period will last for 12 weeks.

Procedures:

1. Intervention layout

- Based on the participant's Ca/Mg intake ratio (obtained from the two 24-hour recalls), the participant will be assigned to a dose that will reduce the Ca/Mg intake ratio to around 2.3 (less than 2.6 but no less than 2.0). Each dose will correspond to one or multiple capsules from three different sizes of magnesium supplementation or placebo.
- Presented in Table E2 is the detailed treatment dosage based on baseline calcium/magnesium ratio and calcium intake level as well as resulting calcium/magnesium ratio after supplementation. Treatment or placebo capsules will be discarded if they are not used within 6-months.

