- Based on the participant's Ca/Mg intake ratio and a table provided by the PI of this study, the research staff will devise standard operating procedures for the Vanderbilt Investigational Drug Service (VIDS) to follow with regard to preparing, labeling, blinding, and dispensing study drug.
- The VIDS will retain a secure set of sealed envelopes containing the treatment assignment. These will be opened in the event of a clinical scenario which necessitates unblinding, as determined by the PI and the safety reviewers.

2. Prescription

- A detailed prescription for Pharmacists, including information on calcium intake, calcium and magnesium ratio, genotype, treatment assignment, administration etc, will be provided by [name] or [name].

3. Magnesium capsule and placebo preparation

- The magnesium supplementation and placebo capsules will be made by the Compounding Pharmacist of the Vanderbilt Investigational Drug Service.
- The Vanderbilt Investigational Drug Service (VIDS) will be responsible for the storage, preparation, and labeling of all investigational agents, and for maintaining accurate drug storage and dispensing logs.
- We have chosen to use magnesium glycinate, a form of magnesium that will avoid a laxative side effect. Three sizes of capsules will be used in this study: 515 mg delivering 77.25 mg elemental magnesium (Size 1) in blue opaque; 694 mg delivering 104.1 mg elemental magnesium (Size 00) in orange opaque; and 489 mg delivering 73.35 mg elemental magnesium (Size 1) in green opaque.
- Identical-appearing placebo (made from microcrystalline cellulose) will be made to match these three magnesium capsules (Sizes 00 orange opaque, 1 blue opaque, and 1 green opaque).

4. Dispensation

The whole intervention period lasts for 12 weeks. Participants will take either magnesium or placebo capsules once per day. Participants will be given the magnesium or placebo capsule at the Clinical Research Center (CRC) during the first clinic visit (week 0), and the second clinic visit at the trial, (week 6).

1st time to dispense the capsules (during the first clinic visit at the beginning of the intervention, week 0)

- Research staff notify Vanderbilt Investigational Drug Service (VIDS) to anticipate a prescription for the day of participant's baseline visit (week 0).
- Research staff provide the physician with the information necessary to complete a prescription.

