Size 1 green opaque: 489 mg delivering 73.35 mg elemental magnesium

Size 1 green opaque: 489 mg delivering 75.55 mg elemental magnesium
Size 1 blue opaque: 515 mg delivering 77.25 mg elemental magnesium

Size 0 orange opaque: 694 mg delivering 104.10 mg elemental magnesium

Row in green only for men

5. Treatment of side effects of magnesium supplements:

- When a study participant reports a side effect of diarrhea from taking the study supplement, the participant will be instructed to take Loperamide (ImodiumTM), according to the manufacturer's directions for no more than 7 days.
- If the Loperamide is not effective within 48 hours of beginning the dosing of Loperamide, the participant will call the study staff. The supplement dose reduction plan will be initiated (see attached table).
- After 7 days of use the participant will be contacted. If the diarrhea has resolved while taking the Loperamide the participant will be instructed to continue to take the prescribed dosage of the study supplement.
- When diarrhea recurs after stopping the initial effective use of Loperamide, the participant will be instructed to resume the manufacturer's dosing recommendations until diarrhea resolves and then decrease the dose of the Loperamide until the minimum effective dose is reached. The participant will remain at this minimum dose for the remaining time left in their study participation. If the diarrhea never resolves, the supplementation reduction plan will be initiated (see attached table).
- A participant, who reports side effects of abdominal gas or cramping, will be advised to take simethicone for relief.

Both Loperamide (ImodiumTM) and Simethicone (Gas-XTM, FlatulexTM, GenasymeTM, and MyliconTM) are inexpensive over-the-counter medications that are safe for long-term use and do not alter intestinal absorption patterns.

6. Dose reduction plan:

When a participant reports that the use of Loperamide is not effective within 48 hours or the diarrhea recurs after stopping the initial dose of Loperamide and never resolves by resuming the Loperamide (see the attached flowchart), the supplement dose reduction plan will be initiated (see attached table). Six reduction steps are included in the Dose Reduction Guidelines.

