- After 4 days of initiating the first reduction step, the participant will be contacted. If the reduction of supplement dosing is ineffective, subsequent reduction steps will be implemented and the participant contacted after 4 days of reduction until resolution of the diarrhea is achieved.
- If diarrhea does not resolve within 4 reduction steps, the participant will be referred to the study physician for consultation.
- When the diarrhea resolves during the use of the dose reduction step plan, the participant will be instructed to return to the use of the initial dosing of the supplement.

[figure not shown]

Table Magnesium Dose Reduction Guidelines for PPCCT

Original dosage	First	Second	Third	Fourth	Fifth	Sixth	Seventh	Eighth
B1	End							
77.25	100%							
O1	B1	End						
104.1	25.80%	100%						
G2	G1	End						
146.7	50%	100%						
B2	B1	End						
154.5	50%	100%						
B1O1	O1	B1	End					
181.35	42.60%	25.80%	100%					
O2	O1	End						
208.2	50%	100%						
B1G2	G2	G1	End					
223.95	34.50%	50%	100%					
O1G2	O1G1	G2	O1	G1	End			
250.8	29.20%	17.30%	29.04%	29.50%	100%			
B3	B2	B1	End					
231.75	33.30%	50%	100%					
B2O1	B1O1	B2	O1	B1	End			
258.6	29.90%	14.80%	32.62%	26%	100%			
B1O2	O2	B1O1	B2	O1	B1	End		
285.45	27.10%	12.90%	14.80%	32.62%	26%	100%		
G4	G3	G2	G1	End				
293.4	25%	33.33%	50%	100%				
O3	O2	O1	End					
312.3	33.33%	50%	100%					
B3O1	B2O1	B1O1	B2	O1	B1	End		
335.85	23%	29.90%	14.80%	32.62%	26%	100%		
B2O2	B1O2	O2	B1O1	B2	O1	B1	End	
362.7	21.30%	27.10%	12.90%	14.80%	32.62%	26%	100%	
B1O3	O3	B1O2	O2	B1O1	B2	O1	B1	End
389.55	19.83%	8.60%	27.10%	12.90%	14.80%	32.62%	26%	100%

Size 1 green opaque: 489 mg delivering 73.35 mg elemental magnesium

Size 1 blue opaque: 515 mg delivering 77.25 mg elemental magnesium

Size 00 orange opaque: 694 mg delivering 104.10 mg elemental magnesium

F. Clinical Visits

1. Clinic Visits

Eligible participants will be invited to the Clinic Research Center, Vanderbilt University Medical Center three times during the period of 12-week intervention, prior to the treatment (week 0), the midpoint (week 6) and the end of intervention (week 12). In addition, the participants will be invited to undergo magnesium tolerance test at the Vanderbilt CRC following the completion of the 12-week intervention with magnesium supplements.

--- Clinic Visit #1

Location

Clinic Visit #1 will be in the Clinical Research Center (CRC) at Medical Center North, 3rd floor on the Vanderbilt Campus

Scheduling

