Magnesium has been widely used in clinical practice and tested in previous clinical trials; it has been well tolerated in previous clinical trials and the reported rate of adverse events has been low. No severe adverse event has been observed even when it was administered intravenously among pregnant women. On the other hand, magnesium supplementation improves insulin resistance and reduces insulin level. Growing evidence from studies conducted in Western societies has linked low intake of magnesium to insulin resistance and systemic inflammation and, thus, risk of diseases common in Western countries, such as type II diabetes, coronary heart disease, and recently colorectal cancer. Magnesium supplementation improves insulin resistance and reduces insulin level. According to data from the US National Health and Nutrition Examination Survey (NHANES), 1999-2000, 79% of US adults do not meet the Recommended Dietary Allowances (RDA) of magnesium. In our proposed study, the dose of magnesium supplementation is personalized based on the current intake ratio; thus, the dose used is generally smaller than that used in most previous studies. Each dose will not surpass the sex- and age-specific DRI for magnesium by more than 100mg/day. Furthermore, we use additional exclusion criteria to avoid potential side effects for subgroups of participants, including potential drug-magnesium interactions, providing additional assurance for the safety of participants. Our protocol enrolls patients believed to be healthy. As an alternative, participants may choose to temporarily or permanently stop supplementation if they feel a complication is unacceptable.

A possible complication of venipuncture is bleeding or the development of a small hematoma at

the point of needle insertion. Blood will be collected from the arm using standard sterile techniques and equipment, and direct pressure at the point of injection will stop this bleeding. Occasionally blood collection will cause a small hematoma, which will heal without permanent damage.

The dietary assessment (i.e., 24-hour recall), and measurement of height, weight, and body circumferences, and urine collection, present no physical risks.

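### Table E2, baseline ratio 3.6-3.8 at 1800 mg calcium: the listed 2 blue capsules give a Ca/Mg ratio of 2.81, not the printed 2.51, and miss the protocol's limit of less than 2.6

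*Combined protocol and SAP*

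**What the plan says.** The dosing rule is in section 6.0, part E, Intervention Protocol: from the two baseline recalls the participant is "assigned to a dose that will reduce the Ca/Mg intake ratio to around 2.3 (less than 2.6 but no less than 2.0"). Part C, Dietary Intake Assessment Protocol, states the same purpose for those recalls: "to determine the appropriate dose of magnesium supplementation in the treatment arm to reduce the ratio to < 2.6".

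The rule is carried out through Table E2: "Presented in Table E2 is the detailed treatment dosage based on baseline calcium/magnesium ratio and calcium intake level". The table crosses 25 baseline-ratio bands with 14 calcium levels (700 to 2000 mg) and prints, for each cell, the capsules and the expected ratio. Three cells of band 3.6-3.8 matter here:

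| Calcium (mg/day) | Capsules listed | Printed ratio |
|---|---|---|
| 1800 | 2 blue | 2.51 |
| 1900 | 3 blue | 2.55 |
| 2000 | 3 blue | 2.59 |

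Pharmacy procedures are to be written from the participant's ratio and "a table provided by the PI of this study". The text does not say whether that table and Table E2 are the same document.

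**The concern.** Two blue capsules at 1800 mg cannot produce almost the same ratio as three blue capsules at 1900 mg. The listed dose also drops sharply and then recovers along the band: 293.4 mg at 1700 mg calcium (4 green), 154.5 mg at 1800 and 231.75 mg at 1900. Either the capsule count or the printed ratio is wrong.

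A ratio below 2.6 is the intervention that Aim 1 sets out to test. A participant in the magnesium arm who was dosed as this cell reads would be analysed as treated while, by design, staying above the target. The printed ratio looks compliant, so a reader who checks only that column would not see the problem.

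**Working it through.** **Inputs.** Elemental magnesium per capsule (Intervention Protocol, item 3): blue 77.25 mg, orange 104.1 mg, green 73.35 mg. Bands, calcium levels, capsule counts and printed ratios are from Table E2.

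**Formula.** Resulting ratio = Ca / (Ca / baseline ratio + supplemental Mg), with the band midpoint as baseline ratio.

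**Does this reproduce the table?**
- 2.6-2.8 at 700 mg, 1 blue: 700/(700/2.7 + 77.25) = 2.08; printed 2.08.
- 3.0-3.2 at 1800 mg, 2 blue: 1800/(1800/3.1 + 154.5) = 2.45; printed 2.45.
- 3.6-3.8 at 1900 mg, 3 blue: 1900/(1900/3.7 + 231.75) = 2.55; printed 2.55.
- 3.6-3.8 at 2000 mg, 3 blue: 2000/(2000/3.7 + 231.75) = 2.59; printed 2.59.

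Over all 25 x 14 = 350 cells, 339 printed ratios agree within 0.015, so this is the table's own method.

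**The cell as listed: 3.6-3.8 at 1800 mg, 2 blue (2 x 77.25 = 154.5 mg).**
- Midpoint: 1800/(486.49 + 154.5) = 2.81; printed 2.51.
- Bottom of band: 1800/(1800/3.6 + 154.5) = 2.75.
- Top of band: 1800/(1800/3.8 + 154.5) = 2.87.

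How intakes between two columns are assigned is not stated. Taking the widest case, 1701 mg at baseline 3.6 gives 2.71 and 1899 mg at baseline 3.8 gives 2.90. No assignment brings the listed dose under 2.6.

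**The same cell with 3 blue (3 x 77.25 = 231.75 mg).**
- Midpoint: 1800/(486.49 + 231.75) = 2.51, the printed figure.
- Across the band: 2.46 to 2.55. At 1899 mg and baseline 3.8 it is 2.596, still below 2.6.

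**Shortfall.** 231.75 - 154.5 = 77.25 mg/day, which is 33% of the 3-blue dose. The planned fall in ratio is 3.70 - 2.81 = 0.89 instead of 3.70 - 2.51 = 1.19, about 75% of it.

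**The other mismatches.** Eleven cells miss by more than 0.015. The other ten compute to between 2.23 and 2.40, inside the window. This is the only cell printed below 2.6 that computes to 2.6 or more.

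**The case against.** The strongest reply is that the case rests on one digit in a table read by machine from a PDF. The same legend gives the green capsule as both 73.35 and 75.55 mg, so a misread is possible. That stands, and is why the remedy starts with a look at the source. It does not dispose of the point: four of the mismatched cells in band 3.4-3.6 (1000, 1100, 1300 and 1700 mg) repeat the dose and ratio of band 3.2-3.4 exactly. A scanning fault would not readily do that, so slips in the source table are plausible too, although that copying does not itself explain this digit.

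It can also be said that other steps lie between the cell and a participant. The written rule requires a ratio below 2.6, the prescription carries the participant's calcium intake and ratio, and a physician signs it. This also stands: a reader might infer that participants were under-dosed, but the documents do not show what was dispensed.

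Three broader readings are tempting and are not supported.

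- **That the table breaks its limit generally.** It openly prints ratios of 2.6 or more in 39 cells at the top dose of 389.55 mg, up to 3.05. Those cells show a ratio their dose does deliver and are a separate matter. The cell at issue prints a ratio its dose cannot deliver, in a band that already uses a larger dose at 1700 mg.
- **That band 2.8-3.0 at 1800 mg fails as well.** One blue gives 1800/(1800/2.9 + 77.25) = 2.58, as printed, and meets the rule by the table's midpoint method. It exceeds 2.6 only for baseline ratios above about 2.93.
- **That the trial result is biased.** Placebo capsule numbers are set from the same baseline ratio, and allocation is random within genotype, so the arms stay comparable.

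**Conclusion.** The cell is internally inconsistent and, as listed, breaches the protocol's own limit: 2.81 (2.75 to 2.87 across the band) against less than 2.6. The capsule count is the likelier error, since 3 blue reproduces the printed ratio and is the dose at the next two calcium levels.

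Severity is minor. The documents give no participant numbers per cell. Purely as an illustration, an even spread of 288/2 = 144 active-arm participants over 350 cells would put 144/350, about 0.4, in any one cell, and none is quite possible. No effect on power, on the estimate or on safety is shown.

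The conclusion assumes that the extracted text shows the cell correctly and that the table was built on band midpoints, which 339 of 350 cells bear out.

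A side note only: band 2.8-3.0 at 2000 mg (1 blue) is printed as 2.6 and computes to 2000/(2000/2.9 + 77.25) = 2.61, which is not below 2.6. Eligibility requires calcium under 2000 mg/day, so it matters only if intakes just under 2000 mg are assigned to that column.

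**What to change.** 1. Compare the 3.6-3.8 / 1800 mg cell with the source table and with the pharmacy procedures drawn from the investigator's table.
2. If it reads 2 blue, change it to 3 blue (231.75 mg; 2.51, and 2.46 to 2.55 across the band). If any participant was dosed from it, record this.
3. Before changing it, check the cell against the legend entry "Row in green only for men" (the colour is lost in this text) and the two dose limits: "supplementation of magnesium will not exceed the DRI for supplemental magnesium intake by more than 40 mg" (section 1.0) and "Each dose will not surpass the sex- and age-specific DRI for magnesium by more than 100mg/day" (section 7.0). Three blue is less than the 293.4 mg already listed at 1700 mg in the same band.

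Optional: in band 2.8-3.0 at 2000 mg, 1 orange (104.1 mg) gives 2000/(2000/2.9 + 104.1) = 2.52 and would meet the rule. Band 2.8-3.0 at 1800 mg needs no change.

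The cost is one look-up and one table cell. Three blue is already among the combinations in the table "Magnesium Dose Reduction Guidelines for PPCCT", so no new capsule or dose-reduction step is needed.

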A randomized controlled study is one in which there are two groups, one treatment group and one control group. The treatment group receives the treatment under investigation, and the control group receives placebo. Assigning patients at random reduces the risk of bias and increases the probability that differences between the groups can be attributed to the treatment. Randomization is used to determine who will receive the magnesium supplement and who will receive placebo treatment.

This study will enroll 288 participants with colorectal hyperplastic polyp or/and adenoma, polyps free but being at high risk of colorectal polyps or cancer. 152 of whom have the GG genotype and 136 of whom have GA/AA genotype. Within the two genotype groups, a permuted-block randomization algorithm will be used to allocate the subjects into the treatment/placebo arm.

Finally, these participants will be randomized to either treatment or placebo using a double-blind two-factorial (Ca/Mg intake ratio and genotype) design so that each treatment/placebo arm will contain 60 participants with the GG genotype and 60 participants with at least one A allele.

Procedures

- The Principal Investigator will generate a list of the 288 participants, 152 of whom have the GG genotype and 136 of whom have GA/AA genotype.
- [name], the co-PI, will conduct the randomization and provide a script to randomly allocate the participants into each treatment/placebo arm within the two genotype groups.
- Each treatment/placebo arm will contain 60 participants with the GG genotype and 60 participants with at least one A allele.
- Both the participants and the study staff will be blind to randomization status until the conclusion of the study. Pharmacists are un-blinded to randomization status and treatment assignment.

Intervention Protocol

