- After the physician has signed the prescription and the participant has provided written informed consent, the research staff fax the prescription and copy of signed consent form to Vanderbilt Investigational Drug Services (VIDS) during the first clinic visit (day 1, week 0).
- VIDS Call the research staff and send the Mg/placebo capsules to CRC on the day of appointment. The research staff gives the participant capsules at the Clinical Research Center of Vanderbilt University Medical Center and an Instruction for taking pill sheet (Appendix E) will be given to the participant and taken home.
- Pharmacist will send magnesium or placebo capsules to participants by Fedex if the participant leaves clinic visit prior to dispense.

2nd time to dispense the capsules (During the second clinic visit, week 6)

- Research staff notify Vanderbilt Investigational Drug Service (VIDS) to anticipate a prescription for the day of participant's second visit (week 6)
- Research staff provides the physician with the information necessary to complete a prescription.
- After the physician has signed the prescription, the research staff fax the prescription to Vanderbilt Investigational Drug Services during the second clinic visit (week 6).
- VIDS Call the research staff and send the Mg/placebo capsules to CRC on the day of appointment.
- The research staff gives the participant capsules at the Clinical Research Center of Vanderbilt University Medical Center and an Instruction for taking pill sheet (Appendix E) will be given to the participant and taken home.

- Pharmacist will send magnesium or placebo capsules to participants by Fedex if the participant leaves clinic visit prior to dispense.

If needed, an extra supply of Magnesium/Placebo supplements will be sent to the participants by Fedex to make participants have enough until their clinic visit.

sure
pills

[figure not shown]

Figure E2. The planned study design

Table E2. Magnesium treatment dosage based on baseline Ca/Mg ratio and calcium intake level and estimated Ca/Mg ratio after use of magnesium supplementation.

Baseline Ca/Mg ratio	Ca intake (mg/day)	Treatment dosage (pill size * number)	Resulting ratio	Ca intake (mg/day)	Treatment dosage (pill size and number)	Resulting ratio
2.6-2.8	700	size 1 (blue)*1	2.08	1400	size 00*1	2.25
2.6-2.8	800	size 1 (blue)*1	2.14	1500	size 00*1	2.27
2.6-2.8	900	size 1 (blue)*1	2.19	1600	size 00*1	2.3
2.6-2.8	1000	size 1 (blue)*1	2.23	1700	size 00*1	2.32

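### Group-level interim results may reach the PI who guides the analysis, against the plan's own blinding statement; the prescription route also needs a clarifying sentence

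*Combined protocol and SAP*

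**What the plan says.** **Interim data.** The same paragraph appears in Section 6.0 I (Data Analysis) and Section 9.0 (Statistical Considerations). Interim analyses may be run whenever required over the five years, for example to support a grant application. A biostatistician from outside the team runs them on unblinded data. The whole study team is to stay blind until the trial is complete. The next sentence allows summaries at study-group level to be passed to the study PIs, for use only in planning other studies. Section 6.0 I adds that one PI conducts or guides all statistical analyses.

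**Blinding and prescription.** Under Randomization Protocols (Section 6.0 E): "Both the participants and the study staff will be blind to randomization status until the conclusion of the study". The next sentence reads: "Pharmacists are un-blinded to randomization status and treatment assignment". The Intervention Protocol adds that "neither participants nor research staff who interacts with the participants or their samples will be aware of the treatment assignments". Item 2, Prescription, then states: "A detailed prescription for Pharmacists, including information on calcium intake, calcium and magnesium ratio, genotype, treatment assignment, administration etc, will be provided by" one of two people, names removed. Item 4, Dispensation, says: "Research staff provide the physician with the information necessary to complete a prescription". After the physician signs at week 0, "the research staff fax the prescription and copy of signed consent form to Vanderbilt Investigational Drug Services", and a similar fax step follows at week 6. The procedures for Clinic Visits #1 and #2 repeat the fax step. As safeguards, "The VIDS will retain a secure set of sealed envelopes containing the treatment assignment", and the pharmacy is to receive operating procedures "to follow with regard to preparing, labeling, blinding, and dispensing study drug".

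**The concern.** The interim paragraph promises a blind team and then makes an exception for the PIs, one of whom directs the final analysis. Section 9.0 leaves several analysis decisions to be taken later. If they are taken after that PI has seen results by group, nobody can show that they were made without knowledge of which choice favours magnesium. The analysis would lose that protection even though no participant's arm had been revealed.

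The prescription raises a smaller question of the same kind. A document listing the arm is described in one item, and two items later research staff who must be blind handle a document called by the same name. What would be exposed is data that depend on staff contact or judgement: pill counts, adverse-event and compliance calls, and ratings of severity and relation to the intervention.

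**Working it through.** No arithmetic applies, because the documents give no figure from which a bias could be derived. The check sets the sections side by side.

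**Interim summaries**

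1. *Who must be blind.* Every study team member, until completion (Sections 6.0 I and 9.0). A PI is a team member.
2. *What may be released.* Group-level summaries from unblinded data, to the PIs. I read study group as randomised group, since summaries pooled over arms would not need unblinded data.
3. *How often.* No number or timing is set.
4. *Who receives them.* The study PIs, in the plural. Section 6.0 I places all analyses under one PI. Names are removed, so it cannot be seen whether that PI would be a recipient, but no wording excludes it.
5. *What is still open.* If normality fails, Section 9.0 allows either a transformation or non-parametric methods. It allows ANOVA or ANCOVA with no rule for choosing. The ANCOVA covariates include intakes of other nutrients, which are not listed. No date is given by which these choices are fixed.

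Taken together, one person could hold group results and then make the choices in step 5. Restricting the purpose of the summaries limits their use, not what the recipient knows.

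**Prescription**

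Two readings fit the text.

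- *One document.* Item 2 is the only description of what a prescription contains, and the staff fax is the only transmission described. The sealed envelopes are for clinical situations that require unblinding, not for routine supply. On this reading staff could see the arm at weeks 0 and 6, which is two of the three intervention visits, since no capsules are dispensed at week 12.
- *Two documents.* Item 2 concerns a prescription meant for pharmacists and supplied by one of two particular people. The clinic document is completed and signed by a physician and is elsewhere called a prescription note. Staff who do not know the arm cannot supply it. A co-PI conducts the randomisation, so someone outside the pharmacy may hold the allocation. On this reading the blind holds, and the item 2 prescription is itself how the pharmacy learns the arm.

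The text does not choose between them, and nowhere states that the faxed form omits the arm. The content of the pharmacy procedures is not given.

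**What would be affected.** Under the one-document reading, research staff count pills at weeks 6 and 12, and research staff or a nurse make the calls on the day after each visit (Section 6.0 F and G). The six scheduled monitoring calls may be made by survey-unit staff instead. The tissue endpoints are largely protected: the pathologist is blinded to treatment and genotype, and scoring uses image analysis (Section 6.0 F, Rectal Biopsy).

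**The case against.** The interim exception is openly declared. It is confined to group level and to planning other studies, the work is done by an outside biostatistician, and there is no intention to stop the trial. The documents do not show that the PI guiding the analysis would receive the summaries. The harm also depends on analysis choices having been left open, which is a weakness in its own right. All of this is correct. It does not reconcile the exception with the statement that the whole team stays blind, nor keep group results from that PI. It does show that fixing the choices early would remove most of the harm.

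On the prescription, the two-document reading is at least as natural as the other, and the names that would settle it were removed before publication. That stands, and it is why this part is secondary. A reader might infer that clinic staff see the arm of every participant. The documents do not support this, because it needs the one-document reading, which is not stated.

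A reader might also infer from the annual report on safety and efficacy (Section 8.0, on reporting adverse events) that the principal investigator sees efficacy by arm each year. Nothing there indicates by-arm reporting, and the blinding statement points to pooled figures.

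**Conclusion.** The interim rule should be changed. As written, the stated blinding is not delivered: group results, with no limit on the number of releases, may reach the PI who conducts or guides the analysis while the choice of scale, test and covariates is open. This assumes that group-level means by randomised arm and that this PI, not being excluded, may be a recipient. The size of any bias cannot be computed. The loss is that the final analysis could not be shown to have been chosen without knowledge of the results. Individual assignments are not at issue.

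The prescription part is a gap in the description, with low to medium confidence that it is more than that. It becomes a route to unblinding at weeks 0 and 6 only if the prescription listing the arm is the one that staff handle. Its effect would then fall mainly on adverse-event and compliance data, not on the tissue endpoints.

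**What to change.** **Interim data (Sections 6.0 I and 9.0, both copies).** State that no by-arm summary goes to the PI who guides the analysis before database lock. Failing that, fix the transformation rule, the test, the model and the covariate list in writing before the first by-arm summary is released to any PI. Reword the sentence on team blinding so that it matches whichever rule is adopted. Cost: a few sentences and, under the first option, a delay in that PI's use of this trial's by-arm data for grant planning.

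**Prescription (Section 6.0 E, items 2 and 4, and Clinic Visits #1 and #2).** State that the form signed and faxed in the clinic carries only the participant or randomisation number plus capsule colours and count. Active and placebo capsules look identical, and capsule number is set from dietary intake in both arms (Section 6.0 C), so this does not disclose the arm. State also that the assignment reaches the investigational pharmacy separately, from the person who holds the allocation list and has no participant contact. Simply deleting treatment assignment from item 2 is not enough: if the documents are separate, that could remove the only routine source of the arm described for the pharmacy. Cost: wording only.
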